7.2. Rimegepant and pregnant women

There are no adequate data on the developmental risk associated with the use of rimegepant in pregnant women. In animal studies, oral administration of rimegepant at high doses (300 mg/kg/day; exposures over 200 times that observed in humans administered at the therapeutic dose of 75 mg) during organogenesis resulted in adverse effects on development in rats (decreased fetal body weight and increased incidence of fetal variations). These highest-dose test exposures also resulted in maternal toxicity and were approximately 45 times the maximum recommended human dose.¹⁴

As of 31 May 2020, there were 32 women treated with rimegepant who reported pregnancies during the rimegepant clinical development program (in addition to 1 pregnancy reported in a partner assigned to rimegepant). Of these 32 treated women, 11 reported live births (in addition to 1 partner pregnancy), 6 reported spontaneous abortions (SABs), 3 reported elective abortions, 4 had subsequently negative urine or serum pregnancy test results, and the 8 remaining women had unknown pregnancy outcomes and/or only an approximate due date was reported with no further follow-up information. There were 4 women assigned to placebo who reported pregnancies (in addition to 1 partner pregnancy), 2 had subsequent negative urine pregnancy test results, and 1 had an unknown pregnancy outcome.

Lastly, a study of breastfeeding women (lactation) with rimegepant (BHV3000-115) was initiated in Jan 2020.

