9.7.3.3. Calculation of outcome prevalence

Prevalence rates of the outcomes of interest will be calculated according to the conventions described in Table 4. In general, the prevalence of each outcome will be calculated by dividing the number of cases of the outcome by the appropriate denominator for that particular outcome, based on clinical knowledge and/or the methodology used by the external comparator. Prevalence is preferred over incidence when examining pregnancy outcomes, such as congenital malformations, because incidence cannot be reliably estimated given the complexities in the reproductive process.⁶⁷

For most outcomes, the main analysis population (denominator) will be the number of pregnant women with pregnancy outcome data, the number of live births, or the number of infants with follow-up data at the timepoint of interest, as appropriate; however, for some outcomes, the main analysis population (denominator) will be restricted based on certain relevant factors:

- For MCM, prevalence in the rimegepant-exposed cohort will be calculated among the subset of women who are exposed during the first trimester.
- For MCM, prevalence will be calculated among live births for the primary analysis, and a secondary analysis will be conducted among live births and fetal losses.
- For preterm birth, SGA, and postnatal growth deficiency, prevalence will be calculated among singleton live births due to the higher risk of these outcomes in twins and higher-order multiples.
- For live birth and infant outcomes (ie, preterm birth, SGA, postnatal growth deficiency, and infant developmental delay), prevalence will be calculated among live births/infants without MCMs.
- For postnatal growth deficiency, infants born preterm or SGA will be excluded from the main analysis population (denominator).
- For infant developmental delay, infants born preterm will be excluded from the main analysis population (denominator).
- For SAB and preterm birth, prevalence will be calculated among the subset of women who are enrolled in the registry prior to 20 and 37 gestational weeks, respectively.
- For some outcomes, prevalence will be calculated at multiple timepoints. For example, postnatal growth deficiency and infant developmental delay will be assessed at 2, 4, 6, and 12 months of

PFIZER CONFIDENTIAL

infant age. At each timepoint, prevalence will be calculated among infants with data available for the particular outcome at that timepoint.

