For comparison with external comparators, the prevalence rates of the outcomes of interest among the rimegepant-exposed participants of the main analysis population will be calculated according to the conventions used by the selected external comparators. For example, for the comparison with MACDP, live births and stillbirths with MCMs (including MCMs not associated with medication exposure) will be included in the numerator, and the denominator will be the number of live births. The MACDP calculates rates by this convention, which increases sensitivity. Likewise, for comparisons with the external cohort of pregnant women without migraine (from the retrospective pregnancy outcomes study), the conventions used to calculate outcome prevalence rates in the internal and external cohort will be aligned.

In addition, "crude" prevalence rates, without limitations and exclusions, may be conducted to avoid restricting the main analysis population (denominator). For example, infants with MCM and/or infants born preterm may be included for the prevalence rate calculation of infant developmental delay.

Outcome	Numerator	Denominator	
Primary Outcome – MCM			
Primary analysis: among live births with 1 st trimester exposure (if applicable for cohort)	Live births with confirmed MCMs (excluding MCMs not associated with medication exposure) among women with pregnancy outcome data and exposure during 1 st trimester (if applicable)	Live births among women with pregnancy outcome data and, if applicable, exposure during 1 st trimester	
Secondary analysis: among all pregnancy outcomes with 1 st trimester exposure (if applicable for cohort)	Live births and fetal losses with confirmed MCMs (excluding MCMs not associated with medication exposure) among women with pregnancy outcome data and, if applicable, exposure during 1 st trimester	Live births and fetal losses among women with pregnancy outcome data and, if applicable, exposure during 1 st trimester	
Secondary analysis: among live births with exposure at any time during pregnancy (if applicable for cohort)	Live births with confirmed MCMs (excluding MCMs not associated with medication exposure) among women with pregnancy outcome data and, if applicable, exposure at any time during pregnancy	Live births among women with pregnancy outcome data and, if applicable, exposure at any time during pregnancy	

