Comparison with external comparator (EUROCAT) ⁴⁴	TOPFA among women with pregnancy outcome data	Live births and stillbirths among women with pregnancy outcome data
Preterm birth		
Primary analysis between internal cohorts	Singleton preterm live births without MCMs among women with pregnancy outcome data who are enrolled (and exposed, if applicable) prior to 37 gestational weeks	Singleton live births without MCMs among women with pregnancy outcome data who are enrolled (and exposed, if applicable) prior to 37 gestational weeks
Comparison with external comparator (Pfizer Study C4951006)	Preterm live births among women with pregnancy outcome data who are	Live births among women with pregnancy outcome data who are

PFIZER CONFIDENTIAL

Outcome	Numerator	Denominator
	enrolled (and exposed, if applicable) prior to 37 gestational weeks	enrolled (and exposed, if applicable) prior to 37 gestational weeks
SGA		
Primary analysis between internal cohorts	Singleton live births without MCMs who are SGA based on weight/length/head circumference among women with pregnancy outcome data	Singleton live births without MCMs with weight/length/head circumference data among women with pregnancy outcome data
Comparison with external comparator (Pfizer Study C4951006)	Live births who are SGA based on weight among women with pregnancy outcome data	Live births among women with pregnancy outcome data
Postnatal growth deficiency		
Primary analysis between internal cohorts (at 2, 4, 6, and 12 months)	Singleton infants without MCMs who were not born preterm or SGA with postnatal growth deficiency based on weight/length/head circumference among infants with weight/length/head circumference data at the time point	Singleton infants without MCMs who were not born preterm or SGA with weight/length/head circumference data at the time point
Infant developmental delay	-	
Primary analysis between internal cohorts (at 2, 4, 6, and 12 months)	Infants without MCMs who were not born preterm with developmental delay in a particular category among infants with developmental milestone data for the category at the time point	Infants without MCMs who were not born preterm with developmental milestone data for the category at the time point

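### The committed analyses of postnatal growth deficiency and developmental delay exclude infants on post-exposure study outcomes, and the all-infant comparison is only optional

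*Protocol*

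**What the plan says.** Section 8.2 sets out to compare the occurrence of the secondary outcomes between exposed and unexposed women with migraine. Section 8.3.2 lists postnatal growth deficiency and infant developmental delay up to 1 year among them. MCM is the primary outcome (8.3.1), and preterm birth and SGA are also secondary outcomes (8.3.2).

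Section 9.7.3.3 narrows the denominators in three steps:

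- For all live birth and infant outcomes: "prevalence will be calculated among live births/infants without MCMs".
- For growth: "For postnatal growth deficiency, infants born preterm or SGA will be excluded from the main analysis population (denominator".
- For delay: "For infant developmental delay, infants born preterm will be excluded from the main analysis population (denominator".

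Table 4 repeats this in the only row given for each outcome. The growth denominator is "Singleton infants without MCMs who were not born preterm or SGA with weight/length/head circumference data at the time point". The delay denominator is "Infants without MCMs who were not born preterm with developmental milestone data for the category at the time point".

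The section gives a reason for excluding multiples (higher risk) but no specific reason for excluding MCM, preterm or SGA infants. After the bullets it allows rates without exclusions as an option, with one example: "infants with MCM and/or infants born preterm may be included for the prevalence rate calculation of infant developmental delay". That option has no Table 4 row and does not appear among the supplementary (9.7.3.6) or sensitivity (9.7.3.7) analyses.

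**The concern.** MCM, preterm birth and SGA become known only after exposure has begun, and the study exists to find out whether rimegepant affects them. A denominator that excludes infants on these conditions conditions on possible effects of the drug. Two consequences follow.

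First, any part of an effect on growth or development that runs through these conditions cannot appear in the restricted RR. For growth the overlap is close: SGA is birth weight below the 10th percentile (9.3.4.8), and postnatal growth deficiency is weight, length or head circumference below the 10th percentile (9.3.4.9). Section 7.2 gives some reason to keep this pathway in view. It reports "decreased fetal body weight and increased incidence of fetal variations" in rats, though at exposures more than 200 times the human level and with maternal toxicity.

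Second, if exposure raises any of the three conditions, more exposed than unexposed infants are removed. The two remaining groups may then no longer be comparable.

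A restricted RR near 1 could be reported as showing no effect on growth or development to 1 year, which is a broader statement than the analysis supports.

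**Working it through.** **Reproducing the plan's figures.** Normal approximation, pooled null variance, two-sided 0.05.

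- MCM, 390 per cohort, 3% v 7.5%: 80.6% (Table 2: 80.6%).
- MCM, 316 per cohort, RR 2.7: 80.1% (Table 2: 80%).
- Evaluable: 390 × 0.9 × 0.9 = 315.9 (stated 316).
- Growth deficiency, 390 per cohort, 10% v 25%: 99.99% (Table 3: >99.0%).

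**How many infants leave.** Inputs: MCM 3%, preterm 8.47%, SGA 10% (Table 3) and 316 per cohort (9.5.2). The three conditions are treated as independent, which is an assumption.

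- Growth, share kept: 0.97 × 0.9153 × 0.90 = 0.799. About 20% are removed and about 253 remain, before multiples and missing data.
- Delay, share kept: 0.97 × 0.9153 = 0.888. About 11% are removed and about 281 remain.
- If exposure raised all three conditions 2.5-fold, the exposed growth share kept would be 0.925 × 0.78825 × 0.75 = 0.547. About 45% are removed and about 173 remain.
- In the same case the exposed delay share kept would be 0.925 × 0.78825 = 0.729, so about 27% are removed.

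**What a purely mediated effect looks like.** The conditional risks below are assumptions; the protocol gives none.

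*Growth, single illustration.* SGA 10% v 20%; deficiency 40% in SGA infants and 8% in others; no other effect.

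- Unexposed: 0.10 × 0.40 + 0.90 × 0.08 = 11.2%.
- Exposed: 0.20 × 0.40 + 0.80 × 0.08 = 14.4%.
- All-infant RR 14.4/11.2 = 1.29. Restricted RR 8%/8% = 1.00.

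*Growth, range.* Hold unexposed deficiency at 10% overall, let the risk a in SGA infants run from 20% to 50%, and set the risk in the others to b = (0.10 − 0.10a)/0.90.

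| SGA in exposed | a = 20%, b = 8.89% | a = 50%, b = 5.56% | Restricted |
|---|---|---|---|
| 20% (doubled) | RR 1.11 | RR 1.44 | 1.00 |
| 25% (2.5-fold) | RR 1.17 | RR 1.67 | 1.00 |

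*Delay.* Preterm 8.47% v 16.94%; delay 5% in term infants.

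- Delay 20% in preterm infants: 0.0847 × 0.20 + 0.9153 × 0.05 = 6.3% v 0.1694 × 0.20 + 0.8306 × 0.05 = 7.5%; RR 1.20.
- Delay 10% in preterm infants: 5.42% v 5.85%; RR 1.08.
- Delay 40% in preterm infants: 7.96% v 10.93%; RR 1.37.
- Restricted RR 1.00 in each case.

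The restricted value of 1.00 follows from assuming no direct effect. It shows what that analysis cannot see and does not predict a result.

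**What remains visible.**

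- A direct effect on growth in the restricted set (about 253 per cohort, 10% reference): power about 88% for RR 2.0 and 99% for RR 2.5.
- The mediators as outcomes in their own right, at 316 per cohort before row-specific exclusions: SGA 10% v 20%, about 94%; preterm 8.47% v 16.94%, about 89%.
- The unrestricted infant outcomes in the single illustrations, at 316 per cohort: growth 11.2% v 14.4%, about 22%; delay 6.3% v 7.5%, about 9%.

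**The case against.** The strongest reply is that the study as a whole would not miss a drug effect through SGA or prematurity. MCM, preterm birth and SGA each have their own internal comparison, with crude and adjusted RR where events permit (9.7.3.1, Table 4). In the illustrations those comparisons have about 94% and 89% power, against 22% and 9% for the unrestricted infant outcomes. This stands. A reader might infer that such an effect is erased from the study, and the documents do not support that. It is absent only from the restricted growth and delay analyses.

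A second reply is that both infant outcomes are defined by chronological age (9.3.4.9, 9.3.4.10), with no correction for prematurity. An infant born early can meet either definition for that reason alone, so an unrestricted comparison partly re-measures preterm birth and SGA. Looking for deficits beyond those already counted is a legitimate aim. This also stands, and it is why the unrestricted analysis should sit beside the restricted one. A reader might conclude that it should replace the restricted analysis as the main one; the documents do not force that choice.

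Other tempting readings go too far:

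- SGA is excluded for growth only.
- The protocol does allow unrestricted rates, so the outcomes are not necessarily analysed only after exclusion.
- The protocol does not say that it suspects an effect on these outcomes, and the animal findings include fetal variations as well as lower fetal weight.
- Exclusion can disturb the balance sought by inverse probability weighting, but nothing shows that it will. Section 9.7.3.4 permits further adjustment for covariates still imbalanced after weighting.

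None of these replies supplies a committed comparison of growth deficiency or delay among all infants, which is what the objective asks for. Separate results for preterm birth and SGA do not show how many more infants have growth deficiency or delay at 12 months.

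**Conclusion.** The concern holds in a limited form. The committed internal analyses of both outcomes condition on post-exposure study outcomes. They estimate the effect not acting through MCM, preterm birth or (for growth) SGA, may be biased by differential exclusion, and do not alone meet the objective in Section 8.2. The unrestricted alternative is optional and is framed as a prevalence rate rather than a between-cohort comparison.

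In the ranges shown, doubling the mediator gives an all-infant RR of 1.11 to 1.44 for growth and 1.08 to 1.37 for delay, with 1.00 in the restricted set. These figures rest on assumed conditional risks and on no direct effect. From the protocol's own rates, and assuming independence, about 20% of unexposed infants leave the growth analysis and about 11% the delay analysis.

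Both are secondary outcomes with nominal p-values (Section 9.7), so the primary conclusion is unaffected. Table 3's growth power uses 390 enrolled women rather than the restricted infants, but at a 2.5-fold effect it still exceeds 99% with about 253 per cohort (99.4%).

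**What to change.** - In Section 9.7.3.3, make the unrestricted analysis a commitment (will, not may) for both outcomes.
- Add Table 4 rows for the unrestricted internal comparison, with crude and inverse-probability-weighted RR: all singleton infants with data at the timepoint for growth, and all infants with data at the timepoint for delay. Report them beside the existing restricted rows.
- Label the restricted rows as the effect not acting through MCM, preterm birth or (for growth) SGA. State that a null result there alone will not be read as no effect on these outcomes.

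The cost is a wording change, two Table 4 rows and a few extra outputs at the final analysis, from data already collected under Section 9.4.1.3. The downside is that the unrestricted estimate partly re-measures prematurity and SGA and has low power for a purely mediated effect. The two analyses should be read together, alongside the separate MCM, preterm birth and SGA results.

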8.2. Objectives

The purpose of the study is to prospectively evaluate fetal, maternal, and infant outcomes through 12 months of age in women with migraine who were exposed to rimegepant during pregnancy or just prior to pregnancy (up to 3 days prior to conception) (hereinafter referred to in the main text as "pregnant women with migraine who were exposed to rimegepant"), as well as in 2 comparison groups of women with and without migraine who were not exposed to rimegepant during pregnancy.

The primary objective is to compare the occurrence of MCMs in the fetuses/infants of women with migraine who were exposed to rimegepant during pregnancy or just prior to pregnancy (up to 3 days prior to conception) to: 1) an internal comparator cohort of women with migraine who were not exposed to rimegepant during pregnancy or just prior to pregnancy (up to 5 product half-lives prior to conception) (hereinafter referred to in the main text as "pregnant women with migraine who were unexposed to rimegepant") and 2) an external comparator cohort of pregnant women without migraine.

The secondary objectives are to compare the occurrence of the secondary outcomes in women with migraine who were exposed to rimegepant during pregnancy or just prior to pregnancy (up to 3 days prior to conception) to: 1) an internal comparator cohort of women with migraine not exposed to rimegepant during pregnancy or just prior to pregnancy (up to 5 product half-lives prior to conception) and 2) an external comparator cohort of pregnant women without migraine.

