9.5.2. Full study

The full study will aim to prospectively enroll a minimum of 390 women with migraine who were exposed to rimegepant during pregnancy or just prior to pregnancy (up to 3 days prior to conception), as well as an internal comparison cohort consisting of 390 women with migraine who were not exposed to rimegepant during pregnancy or just prior to pregnancy (up to 5 product half-lives prior to conception). The target sample size for the registry is based on the primary outcome, MCM, which is also the outcome with the most restrictive denominators and 1 of the lowest prevalence rates in the general population. If all are evaluable for potential MCMs (evaluable being those for whom pregnancy outcome and major/minor congenital malformation assessments are obtained), and assuming an approximate 3% overall population prevalence of MCM, ⁵⁴ at α =0.05, this sample size provides 80% power to detect a 2.5-fold increased risk for overall MCM. Most registry power calculations are performed for overall MCM to detect an increased risk between 2- and less than 3-fold.⁵⁵ A midpoint threshold of a 2.5-fold increased risk was selected for this study. Assumptions for study calculations are consistent with those applied in the retrospective pregnancy outcomes study (NDA 212728, postmarketing requirement 3799-7, Pfizer study C4951006 [formerly BHV3000-403]).

Prospective enrollment can occur only after pregnancy is recognized but while the pregnancy is ongoing. Therefore, early pregnancy losses will not be captured, and a live birth rate higher than that of the general population would be expected. Research shows that approximately 90% of pregnancies enrolled in pregnancy exposure registries result in a live birth.^{56,57} Assuming that 90% of prospectively enrolled pregnancies result in live births and 10% are lost to follow-up,⁵⁸ at α =0.05, the study sample of 390 prospectively enrolled pregnant women in each internal cohort would result in 316 evaluable participants per cohort. Therefore, the study would have 80% power to detect a 2.7-fold increased risk of overall MCM (Table 2).

PFIZER CONFIDENTIAL

Outcome	N per cohort	Reference rate	Relative risk detectable	Power ^b
МСМ	390	3% ^{54,55,59}	2.5	80.6%
МСМ	316 ^a	3% ^{54,55,59}	2.7	80%

Table 2.	Sample Size and Power Estimates for Primary	Outcome, MCM

MCM = major congenital malformation; reference rate = prevalence rate of outcome in general population for pregnant women of any age

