^a Assumes that 90% of prospectively enrolled pregnancies result in live births and 10% are lost to follow-up, resulting in 316 evaluable participants

^b Power calculations based on normal approximation, 2-tailed, α =0.05⁶⁰

Additionally, Table 3 shows that, without any adjustments for multiple comparisons, the proposed sample size (390 pregnant women) will afford the study >80% power to detect a 2.5-fold increase in all other outcomes except eclampsia, stillbirth, and TOPFA (for which the study will have <20% power to detect a 2.5-fold increase).

Table 3.	Power Calculations
----------	---------------------------

Outcome	Reference rate	Power estimate ^a
MCM ^{54,55,59}	3%	80.6%
Gestational diabetes ²⁹	6.9%	>99.0%
Gestational hypertension ⁶¹	6.5%	>99.0%
Pre-eclampsia ⁶²	3.40%	85.5%
Eclampsia ⁶¹	0.3%	2.7% ^b
SAB ⁶³	13.4%	>99.0%
Stillbirth ⁶⁴	0.596%	12.6% ^b
Elective termination ⁶⁵	18.6%	>99.0%
TOPFA ⁶⁶	0.4%	5.8% ^b
Preterm birth ²⁹	8.47%	>99.0%
SGA*	10.0%	>99.0%
Postnatal growth deficiency*	10.0%	>99.0%

MCM = major congenital malformation; reference rate = prevalence rate of outcome in general population for pregnant women of any age; SAB = spontaneous abortion; SGA = small for gestational age; TOPFA = termination of pregnancy for fetal anomaly.

*By Definition

^a Power calculations were conducted using nQuery and were based on normal approximation, 2-tailed, alpha 0.05.

^b Fisher's Exact test was used for power calculation.

PFIZER CONFIDENTIAL

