Secondary analysis: among all pregnancy outcomes with exposure at any time during pregnancy (if applicable for cohort)	Live births and fetal losses with confirmed MCMs (excluding MCMs not associated with medication exposure) among women with pregnancy outcome data and, if applicable, exposure at any time during pregnancy	Live births and fetal losses among women with pregnancy outcome data and, if applicable, exposure at any time during pregnancy	

Table 4.	Calculation of Outcome Prevalence
----------	------------------------------------------

PFIZER CONFIDENTIAL

Outcome	Numerator	Denominator
Comparison with external comparator (CDC MACDP)	Live births and stillbirths with confirmed MCMs (including MCMs not associated with medication exposure) among women with pregnancy outcome data and exposure during the 1 st trimester	Live births among women with pregnancy outcome data and exposure during the 1 st trimester
Comparison with external comparator (Pfizer Study C4951006 [formerly BHVN Outcomes Study])	Live births with confirmed MCMs (excluding MCMs not associated with medication exposure) among women with pregnancy outcome data and exposure at any time during pregnancy	Live births among women with pregnancy outcome data and exposure at any time during pregnancy
Comparison with EUROCAT	Live births and stillbirths and TOPFA with confirmed MCMs (including MCMs not associated with medication exposure) among women with pregnancy outcome data and exposure during the 1 st trimester	Live births and stillbirths among women with pregnancy outcome data and exposure during the 1 st trimester
Secondary Outcomes		
Minor congenital malformations	Live births with minor congenital malformations among women with pregnancy outcome data	Live births among women with pregnancy outcome data
Gestational diabetes		
Primary analysis between internal cohorts	Gestational diabetes among women with pregnancy outcome data	Women with pregnancy outcome data
Comparison with external comparator (CDC NVSS)	Gestational diabetes among live births	Live births among women with pregnancy outcome data
Gestational hypertension		
Primary analysis between internal cohorts	Gestational hypertension among women with pregnancy outcome data	Women with pregnancy outcome data
Comparison with external comparator ⁶¹	Gestational hypertension among live births	Live births among women with pregnancy outcome data
Pre-eclampsia		

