9.7.3.5. Subgroup analyses

Where sample size permits, subgroup analyses will be conducted for all outcomes that consider:

- Timing of exposure (trimester of exposure)
 - For the analysis of MCM, the primary focus will be on exposure during the first trimester.
- Extent of exposure (cumulative dose during pregnancy or relevant exposure window)
- Indication for use of rimegepant (acute only, preventive only, or both)
- Maternal age at conception (<18 years, 18-34 years, and ≥ 35 years)
- For the analysis of MCM, preterm birth status (full term or preterm)

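### The MCM comparison with Study C4951006 in Table 4 counts rimegepant exposure at any time in pregnancy, an unexplained departure from the protocol's first-trimester rule that may bias this one comparison toward the null

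*Protocol*

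**What the plan says.** Section 8.2 gives the primary objective two comparators: an internal cohort with migraine not exposed to rimegepant, and "an external comparator cohort of pregnant women without migraine". Section 9.2.3 builds the second from published US rates among women without migraine and from the comparison population of Study C4951006, which it presents as a supplementary source.

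On the exposure window, Section 9.7.3.3 says: "For MCM, prevalence in the rimegepant-exposed cohort will be calculated among the subset of women who are exposed during the first trimester". Section 9.7.3.5 repeats the emphasis: "For the analysis of MCM, the primary focus will be on exposure during the first trimester".

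Table 4 then sets the window row by row for MCM:

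| MCM row in Table 4 | Exposure window |
|---|---|
| Internal, primary analysis | First trimester |
| Internal, secondary analyses | One first trimester, two any time |
| External, MACDP | First trimester |
| External, EUROCAT | First trimester |
| External, Study C4951006 | Any time |

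The C4951006 denominator reads "Live births among women with pregnancy outcome data and exposure at any time during pregnancy", and its numerator matches. There is no first-trimester version of this row.

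Section 9.7.3.3 also says that external comparisons follow the comparator's conventions, and that conventions will be aligned for C4951006 in particular.

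**The concern.** In the C4951006 row, women first exposed in the second or third trimester count as exposed. If such exposure carries only background MCM risk, their infants move the exposed prevalence toward the comparator rate. In a safety study that is the unfavourable direction, since a real effect looks smaller.

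The row also reverses the protocol's own hierarchy. Internally, any-time exposure is a secondary MCM analysis. For C4951006 it is the only one specified. Table 4 has no MCM row for the published non-migraine rates, so this is the only MCM convention the protocol fixes for a group defined as being without migraine.

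**Working it through.** **1. Does alignment explain the window?** Three observations from the protocol suggest not.
- The population used from C4951006 is women without migraine (Section 9.2.3.2). The rimegepant window applies only to the registry side.
- MACDP and EUROCAT are external background sources too, yet their rows keep the first-trimester limit. The MACDP example in the text concerns which outcomes enter the numerator and denominator, not exposure timing.
- Other C4951006 rows restrict exposure timing: spontaneous abortion to women enrolled and exposed before 20 weeks, preterm birth to before 37 weeks.

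**2. Reproducing the protocol's power figures (Section 9.5.2).** These concern the internal comparison; none is stated for C4951006. Inputs:
- "The full study will aim to prospectively enroll a minimum of 390 women with migraine" who were exposed, with 390 unexposed;
- "assuming an approximate 3% overall population prevalence of MCM";
- "this sample size provides 80% power to detect a 2.5-fold increased risk for overall MCM";
- Table 2 footnote: "Power calculations based on normal approximation, 2-tailed", α = 0.05.

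Power = Φ{ [ |p1 − p0| − 1.96·√(p̄(1 − p̄)(1/n1 + 1/n0)) ] / √(p1(1 − p1)/n1 + p0(1 − p0)/n0) }

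- n = 390 per group, 3% vs 7.5%: (0.045 − 1.96 × 0.01597)/0.01589 = 0.862, power 80.6% (stated 80.6%).
- Evaluable n: 390 × 0.9 × 0.9 = 315.9, i.e. 316. At 3% vs 8.1%: (0.051 − 1.96 × 0.01821)/0.01810 = 0.845, power 80.1% (stated 80%).

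Both figures reproduce.

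**3. Dilution.** Let f be the share of exposed live births with first-trimester exposure. If later-only exposure carries no excess risk:

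RR(any time) = f × RR + (1 − f)

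For RR 2.5 and f = 0.9: 0.9 × 2.5 + 0.1 = 2.35. For f = 0.7: 0.7 × 2.5 + 0.3 = 2.05. The documents do not give f, so a range is shown. Power is illustrated at true RR 2.7, 316 exposed live births and a 3% reference rate; the restricted analysis uses f × 316 exposed.

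| f (assumed) | Any-time RR, true 2.5 | Any-time RR, true 2.7 | Power vs 316: any time / restricted | Power vs comparator 100 times larger (assumed): any time / restricted |
|---|---|---|---|---|
| 0.95 | 2.43 | 2.62 | 77% / 79% | 97% / 98% |
| 0.9 | 2.35 | 2.53 | 73% / 78% | 96% / 97% |
| 0.8 | 2.20 | 2.36 | 65% / 76% | 93% / 96% |
| 0.7 | 2.05 | 2.19 | 56% / 74% | 88% / 94% |
| 0.5 | 1.75 | 1.85 | 35% / 67% | 69% / 87% |

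Under this assumption, restriction has the higher power at every share tabulated, despite fewer infants. The protocol plans exact methods for external comparisons, so these normal-approximation figures show scale only.

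**4. Precision cost of restricting.** At f = 0.8, RR 2.5 and a 3% background, exposed prevalence is 3% × 2.20 = 6.6% any time and 7.5% restricted. The ratio of standard errors is √[(0.075 × 0.925)/(0.8 × 0.066 × 0.934)] = 1.19. If prevalence were unchanged it would be √(1/0.8) = 1.12.

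**The case against.** The strongest reply is that the protocol allows external comparisons to follow the comparator's conventions and promises alignment with C4951006. Other C4951006 rows also depart from their internal counterparts: preterm birth and small for gestational age drop the singleton and no-MCM restrictions. The first-trimester bullet cannot be absolute either, since Table 4 has two any-time secondary MCM rows. This stands in part. A reader might infer an outright contradiction or a proven error, but the documents do not support that: the C4951006 protocol is not shown, so its conventions cannot be checked. What remains is a departure that is not explained and that the alignment clause does not appear to require.

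A reader might also infer that C4951006 is the only non-migraine comparator and that half of the primary objective is diluted. Neither follows. Published non-migraine rates also serve as comparator. The internal comparison is the powered one, and the significance threshold in Section 9.7.3.1 belongs to it; it keeps the first-trimester window. The first-trimester prevalence is already planned in the internal primary row, which otherwise matches the C4951006 row, so a signal would not be hidden. What is missing is the formal first-trimester comparison with C4951006.

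Finally, the size is uncertain. Eligibility from 3 days before conception, and the remark in Section 7 that migraine may become less frequent later in pregnancy, make a high f plausible without proving it. At f = 0.9 the power difference is about 5 points against an equal-sized comparator and about 1 point against a very large one. Background risk after later-only exposure is also an assumption: Annex 4 notes MCMs associated with second- and third-trimester valproate exposure.

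**Conclusion.** The point holds in limited form. The C4951006 row is the only external MCM comparison in Table 4 with an any-time window, and the protocol gives no reason. If excess risk is confined to first-trimester exposure, the comparison is biased toward the null: a true RR of 2.5 reads as 2.35 at f = 0.9 and 2.05 at f = 0.7. The direction rests on that risk assumption and the size on f, which the documents do not give. The reach is the C4951006 part of the second primary-objective comparison and nothing beyond it.

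**What to change.** In Table 4, add an MCM row for Study C4951006 with numerator and denominator both restricted to first-trimester exposure, and name it the main comparison with that study. Keep the existing any-time row as secondary, matching the internal hierarchy. Adding a row, rather than overwriting one, keeps whatever alignment the any-time row was meant to serve. If C4951006's conventions do require the wider window, say why and qualify the first-trimester bullet in Section 9.7.3.3.

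The cost is a table edit, or a sentence or two of text, made before the final comparative analysis. The main comparison would rest on fewer exposed infants: at f = 0.8 and RR 2.5 the standard error of the exposed prevalence is about 19% wider, or 12% if prevalence is unchanged.
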